7.2 Dose Modification

If subjects develop intolerable side effects during the study, the investigator may down-titrate to the starting dose with patient permission.

7.3 Study Drug Dispensing

Study medications and placebos will be dispensed by the University of Minnesota Medical Center, Fairview Investigational Drug Service (IDS) according to the specified blinded randomization protocol at the baseline, 1 month, 3 month and 6 month visits. Study patients

who drop out prior to the 3 month time point will be replaced by alternate patients who meet study criteria and will not toward overall enrollment goal. Each patient will receive one bottle of study medication or placebo, labeled according to applicable regulatory requirements.

7.4 Emergency Treatment Unblinding

The IDS pharmacist will have the ability to unblind for individual patients only in case of an emergency where the further treatment of the patient is dependent upon knowing the study medication that the patient has been receiving. In the event of pregnancy, the patient's treatment assignment will be unblinded due to the potential effect of active medication on the developing fetus.

7.5 Supportive Care Guidelines

All supportive measures consistent with optimal patient care will be given throughout the study.

7.6 Duration of Therapy

Patients will receive protocol therapy for 9 months unless any of the following occurs:

- Patient withdraws consent,
- Continued and/or extreme non-compliance,
- Intercurrent illness that prevents further administration of study drugs,
- Study physician feels study treatment is not in the best interest of the patient,
- Unacceptable adverse events(s).

7.7 Follow-up

Subjects not experiencing adverse events will be considered completed at the 9 month study visit. For patients experiencing adverse events or if treatment related toxicity is present at the final visit, an additional follow-up visit will occur in 30 days (\pm one week).

Patients may continue on treatment beyond study using commercially available drug(s) at the discretion of the treating physician; however drug assignment will not be unblinded until the last patient completes study drug treatment.

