7. TREATMENT PLAN

7.1 Administration Schedule

Depending on assigned treatment group, subjects will take nebivolol, atenolol, or placebo. Matching medications necessary for maintaining the double-blind nature of the study will be provided by Forest, Inc.

Nebivolol 5 mg will be taken once daily with or without food by mouth for the first month. At the 1 month visit, nebivolol will be increased to 10 mg per day and will be taken for up to 8 months.

Atenolol 25 mg will be taken once daily with or without food by mouth for the first month. At the 1 month visit, atenolol will be increased to 50 mg per day and will be taken for up to 8 months.

Placebo will be taken in the same manner as nebivolol and atenolol treatment groups.

Patients will return to clinic at 1, 3, 6 and 9 months (+/- 1 week) for evaluation and a compliance check.

Patients will be instructed to return all study drug bottles and any remaining tablets to each appointment where subject compliance will be assessed by performing tablet counts.

Patients who demonstrate non-compliance during the study will be counseled regarding proper administration of study medication. In cases of continued and/or extreme non-compliance, study participation may be discontinued.

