10. ADVERSE EVENT REPORTING

For serious adverse event reporting purposes, toxicity information will be collected beginning with the 1st dose of study drug and continuing to approximately 30 days after the last dose of study drug or at the time the patient switches to commercially available drug (if patient decides to continue treatment beyond 1 year off study).

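### Section 10 collects serious adverse events to about 30 days after the last dose, but event-free subjects who do not switch to commercial drug have no scheduled contact in that window

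*Combined protocol and SAP*

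**What the plan says.** Five places in the combined protocol and SAP bear on this.

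- **Section 10 (Adverse Event Reporting), start and end of collection.** For SAE reporting, "toxicity information will be collected beginning with the 1st dose of study drug", "continuing to approximately 30 days after the last dose of study drug". The same sentence gives an alternative end: "at the time the patient switches to commercially available drug". Nothing there confines the window to subjects who have already had an event.
- **Section 7.7 (Follow-up), close-out.** "Subjects not experiencing adverse events will be considered completed at the 9 month study visit". The exception reads: "For patients experiencing adverse events or if treatment related toxicity is present at the final visit", "an additional follow-up visit will occur in 30 days", with a tolerance of one week either way. The section also lets patients go on to commercial drug at the treating physician's discretion.
- **Section 7.6 (Duration of Therapy).** "Patients will receive protocol therapy for 9 months unless any of the following occurs". For a full-course subject the last dose therefore falls at about the month 9 visit.
- **Sections 7.1 and 8.1 (visits).** "Patients will return to clinic at 1, 3, 6 and 9 months (+/- 1 week"). The Schedule of Events has no column after month 9, and no telephone call is described.
- **Section 10.5 (reports to the drug supplier).** Any SAE after consent must be reported, within 24 hours of first knowledge. No end date is given, and no means of finding events after close-out is described.

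**The concern.** For a full-course subject, the post-dose window opens at about the visit at which Section 7.7 closes out those without adverse events. The plan states a window and then schedules a contact in it only for subjects selected by what happened to them earlier.

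Two things are at stake. The first is completeness: a subject who is never asked appears in a listing as having no post-treatment SAE, when none was sought. The second is comparability: adverse events can be affected by treatment, so if their rates differ among nebivolol, atenolol and placebo, the share of each arm that is actively followed after the last dose differs too.

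The plan itself treats the month after treatment as relevant. Besides the SAE window, Section 5.1 asks for contraception for one month after dosing ends, and Section 10.5 requires every pregnancy to be reported once the site knows of it. Those duties begin only when the site learns of an event.

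**Working it through.** No stated figure in the plan has to be reproduced. The check sets the window against the contact schedule and then shows how many subjects could be affected.

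**Step 1: window against planned contact, for a subject who completes nine months of drug.**

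| Subject | Window under Section 10 | Planned contact after month 9 |
|---|---|---|
| No adverse event or toxicity; does not switch | about 30 days | none |
| Adverse event, or toxicity at the final visit; does not switch | about 30 days | one visit, day 30 − 7 = 23 to day 30 + 7 = 37 |
| Switches to commercial drug at month 9 | little or none | little or nothing to miss |

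The conflict lies in the first row. In the second row, a visit held on days 23 to 29 also ends a little before day 30, which the word approximately in Section 10 may be meant to allow.

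**Step 2: number of subjects (illustration).** Inputs are the 75 subjects of the accrual goal, a 30-day window, and an event-free share *f*. The documents do not give *f*, so a range is assumed. All subjects are taken to complete treatment and none to switch.

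Subjects without planned contact = 75 × *f*. Person-days without planned contact = 75 × *f* × 30, out of 75 × 30 = 2250.

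| *f* (assumed) | Subjects | Person-days of 2250 |
|---|---|---|
| 0.30 | 75 × 0.30 = 22.5, about 22 | 675 |
| 0.50 | 75 × 0.50 = 37.5, about 38 | 1125 |
| 0.70 | 75 × 0.70 = 52.5, about 52 | 1575 |

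If some of these subjects switch to commercial drug at month 9, the counts fall accordingly. The documents do not give that share either.

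**Step 3: what the wording leaves open.**

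- In the Section 7.7 exception, the reference to the final visit may qualify only the toxicity, in which case any adverse event during the nine months could trigger the extra visit. It may instead qualify both. The broad reading makes *f* smaller and the narrow one larger; the first row of Step 1 exists under either.
- For subjects who stop drug early, the documents do not say whether visits continue. A later scheduled visit might cover their window, so the finding is confined to full-course subjects.
- Section 10 attaches to the switch clause a remark about treatment continuing past one year, which does not fit a nine-month course.

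**The case against.** The strongest reply is that Section 10 defines which events must be reported and does not promise each subject a visit. On that view Section 10.5 covers the gap, because any SAE that becomes known is reportable with no end date, and events such as death or hospitalization often do become known. Some subjects also come from the investigators' own center and the affiliated clinics (Section 5). In addition, the switch clause leaves some subjects with no window to miss.

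Much of this stands, and it rules out several stronger readings.

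- **A reader might infer that the window is observed only in subjects who already had events.** The documents support only that it is actively observed, by a scheduled contact, only in them. Spontaneous reports are not ruled out.
- **A reader might infer that most subjects go unobserved.** No event-free share is given, the trigger for the extra visit is ambiguous, and the assumed range above falls on both sides of one half.
- **A reader might infer a distorted ratio between arms.** Assuming adverse events in 40% of an active arm and 20% of placebo gives 0.40 × 25 = 10 against 0.20 × 25 = 5 subjects followed, a ratio of 2. That ratio only restates one assumed pair of rates. Carrying it over to SAE counts also requires that no event-free subject reports spontaneously and that SAE risk is unrelated to having had an earlier event.
- **A reader might infer that a planned safety comparison is biased.** Sections 9.1 and 9.2 list no safety endpoint and Section 12.1 plans no test of adverse events between arms. The effect is confined to descriptive tabulation.

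The reply does not remove the conflict itself. Spontaneous reporting is not the same as collecting information through a stated window, and switching is optional, so subjects who neither switch nor have events remain without contact.

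**Conclusion.** The point holds in a limited form. As written, the plan cannot actively collect its own post-dose window in full-course subjects who are event-free and do not switch to commercial drug, and active follow-up after treatment depends on earlier adverse events. Any descriptive table of post-treatment SAEs would be incomplete, and could be unequally so across arms if adverse event rates differ.

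The size is uncertain: about 22 to 52 of 75 subjects for an assumed event-free share of 30% to 70%, on the assumptions that all complete treatment and none switch. The direction and amount of any difference between arms cannot be derived from the documents. The primary estimate of change in small artery elasticity is not touched. This is a cheap improvement to safety collection and does not threaten the trial's main result.

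**What to change.** Reconcile Section 7.7, the Section 8.1 schedule and Section 10, in one of two ways.

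1. **Keep the window and observe it.** Add one telephone contact by existing staff, in the existing slot of 30 days plus or minus one week, for every subject whose window has not already ended through a switch to commercial drug. Add it to the Schedule of Events and record the date of any switch. Asking every such subject the same SAE questions removes the dependence on earlier events.
2. **Restate the window.** Change Section 10 to match the follow-up actually planned, and label events after month 9 in event-free subjects as spontaneously reported only.

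Under either option, say whether the Section 7.7 trigger means any adverse event during the study or only one present at the final visit, state what happens to subjects who stop drug early, and clear up the one-year remark in Section 10.

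The first option costs at most one call per subject, so no more than 75 calls for 75 subjects. The second is a change of wording. Neither alters treatment or the primary analysis.

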8. STUDY PARAMETERS

8.1 Schedule of Events

Procedure/measurement	Screen	Baseline	1 Month	3 Months	6 Months	9 Months
Resting blood pressure	x		x	x	x	x
Arterial elasticity (small and large)	x		x	x		x
Treadmill exercise test		x		x		x
Carotid intima-medial thickness		x		x		x
Electrocardiogram		x		x		x
Left ventricle ultrasound		x		x		x
Retinal photo		x		x		x
Flow-mediated dilation		x	x	x		x
Blood draw		x		x		x
Urine sample collection		x		x		x
Physical examination		x		x		x
Medical history		x				

Blood and urine analysis	Code	Baseline	1 Month	3 Months	6 Months	9 Months
Pro-brain natriuretic peptide	ProBNP	x		x		x
Microalbumin, urine	UMA	x		x		x
high sensitivity C-reactive protein	hsCRP	x		x		x
Lipid panel	BLIP	x		x		x
Fasting glucose	Glu	x		x		x
Urine pregnancy test (if appropriate)	HCGU	x				

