6. RANDOMIZATION PROCEDURES

Randomization will occur after informed consent has been obtained and after eligibility is confirmed by measuring blood pressure and small artery elasticity. Two 1:1:1 randomization lists (one for subjects taking a statin and one for subjects without statin therapy) generated by variable block randomization will be used to assign each subject to a study arm at the time of enrollment. This method will allow stratification of statin therapy.

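### Fetal harm is a named risk, but no pregnancy test is scheduled after Baseline during 9 months of drug, even at 3 and 9 months when urine is already collected

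*Combined protocol and SAP*

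**What the plan says.** All references are to the combined protocol and SAP.

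- **Hazard.** 5.2 excludes pregnant and lactating women and gives fetal harm from beta-blockers as the reason.
- **Testing.** In the blood and urine table of 8.1, the row "Urine pregnancy test (if appropriate)" (code HCGU) has one mark, under Baseline. The 1, 3, 6 and 9 month cells are blank. No other section schedules a repeat.
- **Urine.** In the procedures table of 8.1, "Urine sample collection" is marked at Baseline, 3 and 9 months. 8.2 sends samples to a diagnostic laboratory and gives no turnaround time.
- **Exposure.** Treatment lasts 9 months (7.6). Drug is dispensed "at the baseline, 1 month, 3 month and 6 month visits" (7.3). Follow-up visits are fixed in 7.1: "Patients will return to clinic at 1, 3, 6 and 9 months". Both active doses double at the first of these; for nebivolol, "At the 1 month visit, nebivolol will be increased to 10 mg per day".
- **Other protections.** Contraception is required on drug and for a month afterwards (5.1). A pregnancy triggers unblinding (7.4), and it must be reported within 24 hours of awareness and followed to term (10.5). A physician examination is scheduled at 3 and 9 months (8.1, 8.2). Under 7.5, "All supportive measures consistent with optimal patient care will be given throughout the study", which leaves room for a test on suspicion. 7.6 does not name pregnancy as a reason to stop drug, but it includes "Study physician feels study treatment is not in the best interest of the patient".
- **After the study.** 7.7 lets patients go on to commercial drug while assignment stays blinded until the last patient has finished.

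**The concern.** The protocol names the hazard and plans a full response to an on-study pregnancy, but the response begins only when someone knows of the pregnancy. Unblinding and reporting are triggered by knowledge, and stopping drug depends on a physician's judgement that also needs it. Contraception makes pregnancy less likely but detects none. Medical history is taken only at Baseline. The examinations at 3 and 9 months are described as general health checks; they might raise suspicion, but they are not pregnancy checks.

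A pregnancy that neither the woman nor the clinic notices could therefore continue on study drug until dosing ends, with drug handed out again at up to three visits. This is a participant-safety matter only.

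**Working it through.** The plan gives no figure on this point to reproduce. The check has two parts: a reading of the schedule, and a bound on exposure derived from visit spacing.

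**Reading the schedule**

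- Scheduled tests after Baseline: 0 of 4 visits (1, 3, 6 and 9 months).
- Post-baseline dispensing visits with a test: 0 of 3 (1, 3 and 6 months).
- Urine is already available at 3 and 9 months, but not at 1 or 6.
- The blanks do not look like a text-extraction fault. The other five rows of the same table are marked at Baseline, 3 and 9 months; only HCGU stops at Baseline.

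**Longest interval on drug without a scheduled test**

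- As written: 9 months.
- With a 3 month test: max(3, 6) = 6 months. A 9 month test does not change this, because drug ends then.
- The visit window of plus or minus one week can add up to 2 weeks between two follow-up visits.

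**Bound on mean exposure after conception**

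Assumptions, none of them from the documents: conception is equally likely at any time in the 9 months on drug, and nothing except a scheduled test reveals the pregnancy. L is the number of months before a test in which a conception is missed. d is the number of months from test to stopping drug.

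- As written: (9²/2)/9 = 40.5/9 = 4.5 months.
- With a 3 month test: [(9 − L²)/2 + d(3 − L) + (6 + L)²/2]/9.

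| L | d | Calculation | Mean (months) | Reduction from 4.5 |
|---|---|---|---|---|
| 0 | 0 | (4.5 + 0 + 18)/9 | 2.50 | 2.00 |
| 0.5 | 0 | (4.375 + 0 + 21.125)/9 | 2.83 | 1.67 |
| 0.5 | 0.25 | (4.375 + 0.625 + 21.125)/9 | 2.90 | 1.60 |
| 1 | 0 | (4 + 0 + 24.5)/9 | 3.17 | 1.33 |
| 1 | 0.25 | (4 + 0.5 + 24.5)/9 | 3.22 | 1.28 |

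Cross-check: each conception detected at 3 months saves 6 months of drug. So 6 × 3/9 = 2.0 when L = 0, and 6 × 2/9 = 1.33 when L = 1 and d = 0. The whole reduction comes from conceptions in the first 3 months, which are 33% of time on drug, or 22% if the last month before the test is missed.

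**Placebo.** Section 6 specifies "Two 1:1:1 randomization lists", so about one third of participants receive no active drug. Averaged over arms, the means are multiplied by 2/3: 4.5 becomes 3.0, 2.5 becomes 1.67, and 2.83 to 3.22 becomes 1.89 to 2.15 months.

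**Adding tests at 6 months, or at 1 and 6 months (L = 0, d = 0)**

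- Tests at 3 and 6: (3 × 4.5)/9 = 13.5/9 = 1.5 months; longest interval 3 months.
- Tests at 1, 3 and 6: (0.5 + 2 + 4.5 + 4.5)/9 = 11.5/9 = 1.28 months.
- At L = 1 both give 19.5/9 = 2.17 months, so the 1 month test then adds nothing.

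**The case against.** The case for leaving the plan alone has real substance. Exclusion, an entry test, contraception, unblinding, reporting and follow-up to term form a coherent chain, and nothing in the protocol contradicts it. The documents set no standard for how often to test. A physician sees and examines each participant at 3 months, the visit where the extra test would fall, and there is another clinic visit at 6 months. Consent pages are not in the copy reviewed, so women may well be told to report a missed period. The number of women at risk is not given.

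Most of this stands, and it limits the size of the point. It rules out three stronger readings that a reader might infer:

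- *Testing would save 1.3 to 2.0 months of exposure.* The documents do not support this as an expected benefit. The figures require that a pregnancy begun in months 0 to 3 goes unnoticed by the woman and the clinic until month 9, through an examination at 3 months and a visit at 6. The share of pregnancies like that is unknown and may be small.
- *Pregnancy is left unmanaged.* It is not. A known pregnancy is well handled; only scheduled detection after Baseline is missing.
- *Every dispensing visit must have a test.* No such standard appears in the documents.

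What the objection does not remove is that every one of these protections either prevents pregnancy or relies on someone noticing it. At 3 and 9 months a sample is already in hand, so the usual reason for not testing does not apply there. Tests at 1 and 6 months would need new samples, which is a sound reason to treat them differently.

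**Conclusion.** The point holds as an inexpensive safety improvement. It is not a flaw in the trial's validity. The facts are certain: one scheduled pregnancy test, at Baseline, and none afterwards.

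The firm effect of the change is on the schedule: the longest untested interval on drug drops from 9 to 6 months, by virtue of the 3 month test. The exposure reductions derived above are upper bounds. They rest on uniform timing of conception, on no other route of discovery and, for the lower range, on assumed values of L (0.5 to 1 month) and d (0 to 0.25 month). The real gain is modest, and no number of pregnancies can be claimed.

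The 9 month test does not shorten exposure to study drug, but it has its own use. It would bring an unrecognised pregnancy into reporting and follow-up, and it would inform the decision under 7.7 on continuing with commercial drug, which is otherwise taken with assignment still blinded.

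**What to change.** **Core change.** In 8.1, mark HCGU at 3 and 9 months for women of reproductive potential, run on the urine already collected. Add a sentence that the 3 month result is to be known before the 3 month bottle is dispensed where possible, and otherwise acted on as soon as it is available. State that the 9 month result feeds pregnancy reporting, follow-up to term and the 7.7 decision.

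**Cost.** Two marks in the schedule, a short addition to the text, and two inexpensive urine tests per applicable woman. No new visit or sample is needed, and further contact is needed only if a result is positive.

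**Optional.** Tests at 1 and 6 months would cover the remaining two dispensing visits, at the cost of two urine samples not now scheduled. The 6 month test does most of the added work; the 1 month test mainly covers the dose increase. The sponsor and investigator should weigh these.

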8.2 Description of Study Parameters

Resting Blood Pressure: Sitting blood pressure (BP) is measured by standard sphygmomanometry at rest. Blood pressure will be measured 4 times on each arm and averaged. The arm with the highest average will be used to obtain future resting blood pressure values.

Small and Large Artery Elasticity: Radial artery pulse waves are registered with the CV Profiler (Hypertension Diagnostics, Eagan, Minnesota). Small artery (C_2) and large artery (C_1) elasticity are derived from the pulse contour analysis.

Treadmill Exercise Test:

Standing blood pressure is measured before exercise, at the end of a 3-minute workload at 5 METS on the basis of a treadmill speed of 2.3 mph at a slope of 7%, and after a 1-minute recovery period.

Carotid Intimal-Media Thickness: Ultrasound with a Sonosite MicroMaxx unit is employed to measure intimal-media thickness 1 cm distal to the carotid bulb and to identify localized carotid plaques.

Electrocardiogram: A standard 12-lead electrocardiogram is evaluated for evidence of hypertrophy, repolarization abnormalities, or conduction abnormalities.

Left Ventricular Mass Index: Left ventricular (LV) ultrasound is performed with Sonosite ultrasound equipment, and left ventricular mass index (LVMI) is calculated according the formula of Devereux.

Optic Fundus Photo: A retinal photo of each eye will be acquired using a digital camera. Each photo will be used to measure and record vascular structure in the retina.

Flow-Mediated Dilation: Endothelium-dependent flow-mediated dilation (FMD) of the right brachial artery will be measured using a SonoSite MicroMaxx ultrasound unit. Reactive hyperemia will be induced by inflation of a blood pressure cuff on the forearm for 5 minutes. The brachial artery will be scanned continuously in M-mode 30s before and 90s after cuff deflation. These recorded images will be used to obtain artery diameter measurements and compared to a scan taken during resting conditions. This procedure will be repeated after a 10 minute recovery period and the measurements will be averaged.

Blood and Urine Analysis: Blood and urine samples will be tested by Fairview Diagnostic Laboratory at the University of Minnesota. Fairview Labs normal and abnormal test ranges will be used to evaluate test results.

Physical Examination: A study physician will perform a standard physical examination to assess the general health of the subject.

Medical History: Each subject will be asked questions pertaining to their own and familial medical history. Special care will be used to collect any information related to cardiovascular events and risk factors.

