A double-blind, placebo-controlled, randomized study examining the effects of nebivolol compared to atenolol on endothelial function and cardiovascular risk in patients with early vascular disease.

EVIDENCE: Early Vascular Impairment-Determine Efficacy of Nebivolol, Comparator Examination

Principal Investigator: [name]

Co-Investigators: [name], PhD
[name]
[name]

Version Date: January 14, 2014

University of Minnesota Medical School, Cardiology Division

PI Contact Information:

Mail: [name]
[name]

[contact]

[contact]

e-mail: [contact]

Table of Contents

STUDY SCHEMA	3
1. INTRODUCTION AND SCIENTIFIC RATIONALE	4
2. STUDY DESIGN	4
3. METHODOLOGY	4
4. OBJECTIVES	5
5. SELECTION OF PATIENTS	6
6. RANDOMIZATION PROCEDURES	7
7. TREATMENT PLAN	8
8. STUDY PARAMETERS	10
9. STUDY ENDPOINTS	12
10. ADVERSE EVENT REPORTING	13
11. DATA AND SAFETY MONITORING PLAN	16
12. STATISTICAL CONSIDERATIONS	16
13. ADMINISTRATIVE REQUIREMENTS	17
14. REFERENCES	18

STUDY SCHEMA

[figure not shown]
Study Population:

- Males and females between 18 and 80 years of age with early vascular disease
- Borderline blood pressure (120-145/80-90 mm Hg)
- Borderline or abnormal small artery elasticity (C_2) as measured by pulse contour analysis
- Treatment-naïve for all blood pressure medications including diuretics for at least 30 days prior to baseline visit
- No known history of cardiovascular disease

Accrual Goals:

75 patients enrolled.

Treatment Plan:

Schedule of Assessments:

- **Blood pressure at rest at 0, 1, 3, 6 and 9 months**
- **Small artery elasticity (C_2) and flow-mediated dilation at 0, 1, 3 and 9 months**
- **Rasmussen Disease Score assessments** (large artery elasticity, carotid intima-medial thickness, electrocardiogram (ECG), treadmill exercise test and left ventricle ultrasound) **at 0, 3 and 9 months**
- **Cardiac Health Biomarkers** (Total cholesterol, LDL, HDL, triglycerides, glucose, hsCRP, microalbuminuria and NT-proBNP) **at 0, 3 and 9 months**

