1. INTRODUCTION AND SCIENTIFIC RATIONALE

β -blockers have been widely used for the treatment and prevention of cardiovascular disease for more than three decades. In recent years, β -blocker usage has declined as studies have shown that traditional β -blockers have little effect on peripheral resistance, which is increased in individuals with endothelial (vascular) dysfunction [1-3]. Recently, nebivolol, a third generation β -blocker, was approved for use in the United States.

Nebivolol is a highly selective β_1 -blocker with vasodilating effects that reduce peripheral resistance. Vasodilation is mediated by nebivolol's action at multiple points in the nitric oxide (NO) pathway [4]. The NO-mediated vasodilation of nebivolol is novel among β -blockers and is particularly promising as impaired vascular function in patients with cardiovascular disease may be due in part to decreased endothelial NO bioavailability [5]. Studies in patients with hypertension and/or coronary artery disease have shown that nebivolol improves endothelial function while non-vasodilating β -blockers do not [6, 7]. The efficacy of nebivolol on endothelial function in low to moderate risk populations has not been well documented.

We propose to study nebivolol in subjects with early vascular disease, using atenolol as an active comparator, as both drugs are selective β_1 -blockers with no α -blocking capabilities. These drugs differ in the fact that atenolol does not have vasodilating properties [6]. We hypothesize that both drugs will likely lower blood pressure through β_1 -receptor blocking but only nebivolol will improve impaired endothelial function, presumably through NO-mediated vasodilation. A placebo arm will also be employed to further differentiate these two treatment strategies.

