5.1 Inclusion criteria

- Males and females 18-80 years of age
- Borderline blood pressure (120-145/80-90 mm Hg)
- Borderline or abnormal small artery elasticity (C₂) as measured by pulse contour analysis
- Treatment-naïve for all blood pressure medications including diuretics for at least 30 days prior to baseline visit
- Able to walk on a treadmill for 3 minutes
- Female patients with reproductive potential must use an approved contraceptive method if appropriate (for example, intrauterine device [IUD], birth control pills, or barrier device) during and for 1 month after the last dose of study drug.
- Voluntary written informed consent before performance of any study-related procedure not part of normal medical care, with the understanding that consent may be withdrawn by the subject at any time without prejudice to future medical care.

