12.1 Statistical Methodology

The primary analysis of the study is descriptive, to obtain a point estimate and 95% confidence interval of the difference in small artery elasticity (C_2) between nebivolol and atenolol treatment arms and nebivolol and placebo at the end of the observation period (9 months). Point estimates and 95% confidence intervals for the improvement in C_2 within each treatment will also be presented.

Secondary analysis estimating difference in Rasmussen Disease Score (RDS) improvement between the nebivolol and atenolol treatment groups along with nebivolol and placebo groups at the end of the observation period (9 months) will also be completed.

Other secondary analyses include estimates of the associations among changes in RDS as well as risk factor and biomarker measurements from baseline to the 3, and 9 month time points in the two positive comparator groups.

Unpaired t-tests will be used to compare the means of C_2 (small artery elasticity) as well as all RDS test component and biomarker values for each subject group at each time point. Paired t-tests will be used to compare baseline values and values from subsequent time points within one group. A P-value of < 0.05 will be considered statistically significant.

Comparison of sensitivity and variability for C₂ and flow-mediated dilation (FMD) methodologies used in quantifying endothelial function of each group over the 9 month study period will also be included in the secondary analyses. Data will be analyzed within and between test groups with a significance level of $P \leq 0.05$.

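### The baseline resting BP is probably the same reading that chose the arm, so within-group BP change carries a small arm-selection bias; between-group comparisons are unaffected

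*Combined protocol and SAP*

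**What the plan says.** Section 8.2 defines the measurement: "Blood pressure will be measured 4 times on each arm and averaged". It continues: "The arm with the highest average will be used to obtain future resting blood pressure values". It requires no minimum difference between arms and no confirming reading, and it names no visit for the two-arm measurement.

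In the section 8.1 table, the row "Resting blood pressure" is marked at Screen and at 1, 3, 6 and 9 months. Its Baseline cell is empty. The Study Schema at the front of the protocol instead lists "Blood pressure at rest at 0, 1, 3, 6 and 9 months".

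Section 6 places randomization "after eligibility is confirmed by measuring blood pressure and small artery elasticity", so the Screen BP also decides entry, against the window in section 5.1 (120-145/80-90 mm Hg).

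Section 9.2.2 makes change in resting BP from baseline to 3 and 9 months a secondary endpoint. Section 12.1 says how within-group change is tested: "Paired t-tests will be used to compare baseline values and values from subsequent time points within one group". It also plans unpaired t-tests between groups at each time point. Section 1 expects that "both drugs will likely lower blood pressure". No section says whether the baseline BP is the mean of the chosen arm or the mean of both arms.

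**The concern.** The higher of two noisy averages tends to overstate the true level of the arm it came from. If that average is also the reference for change, later readings on the same arm carry fresh error and drift back, with or without treatment. If the reference is the two-arm average, the follow-up readings come from the arm that tends to be truly higher, so they tend to lie above it. In either case the paired t-test compares two different measurements.

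What is at stake is the within-group BP result. With the higher-arm reference, the artefact runs in the direction that section 1 predicts for both active drugs, and it would appear under placebo too. Resting BP is also one of the ten RDS components, so the baseline BP score rests on the same undefined value.

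**Working it through.** **Inputs from the protocol.** Four readings per arm and follow-up on the higher arm only (8.2); no Baseline mark (8.1); paired t-test at 0.05 (12.1, sidedness not stated, two-sided assumed); 25 per group (12.2).

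**The plan's own figure.** There is none for BP. The group size comes from the C2 calculation, which reproduces: 2 × (1.960 + 1.282)² × 3.57² / 3.3² = 24.6, rounded up to 25 per arm. It is used here only to supply n.

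**Is there a separate month-0 BP?** The schema puts BP, C2 and FMD all at month 0. In the 8.1 table, C2 (arterial elasticity) is marked before treatment only at Screen, and FMD only at Baseline. So month 0 in the schema covers either visit and does not establish a fresh BP reading. Screen is the only pre-treatment resting BP in the table, and the two-arm measurement is inferred to take place there.

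**Formulas.** Let s be the error SD of one arm's four-reading mean and t the SD of the true difference between arms. The observed difference has variance t² + 2s². The observed higher-arm mean exceeds the two-arm mean on average by ½ × √(2/π) × √(t² + 2s²). A share t²/(t² + 2s²) of that excess is real and the rest is error. Hence:

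- reference = higher-arm mean: spurious fall = √(2/π) × s² / √(t² + 2s²)
- reference = two-arm mean: spurious rise = √(2/π) × t² / (2√(t² + 2s²))

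**Middle case, s = 3 and t = 4 mm Hg.** √(16 + 18) = 5.83. Fall = 0.798 × 9 / 5.83 = 1.23. Rise = 0.798 × 16 / (2 × 5.83) = 1.09. Simulation agrees (1.23-1.24 and 1.09).

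**False-positive rate.** For n = 25 and SD of change 7-9 mm Hg (assumed), the noncentrality is bias / (SD/5) with 24 df. For the middle-case fall this is 1.23/1.4 = 0.88 at SD 7 and 1.23/1.8 = 0.68 at SD 9, giving rejection rates of 13.5% and 10.1%.

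| s | t | Fall, higher-arm reference (mm Hg) | Rise, two-arm reference (mm Hg) | P<0.05 in an untreated group, from the fall |
|---|---|---|---|---|
| 1.5 | 5 | 0.33 | 1.84 | 5-6% |
| 2 | 4 | 0.65 | 1.30 | 6-7% |
| 3 | 4 | 1.23 | 1.09 | 10-14% |
| 3 | 0 | 1.69 | 0 | 15-21% |
| 4 | 0 | 2.26 | 0 | 23-34% |

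The last row is an extreme. It assumes no true inter-arm difference and, if error comes only from independent readings, a single-reading SD of 4 × √4 = 8 mm Hg.

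**Entry selection on the same reading.** The Screen BP must also fall inside a two-sided window. A separate simulation used single-reading SD 5, extra arm-specific visit error SD 2 and true inter-arm SD 3, where arm selection alone gives a fall of 1.5 mm Hg. Adding a 120-145 systolic window moved the total to a fall of between 0.3 and 4.2 mm Hg, depending on the assumed population mean (120-135) and visit-to-visit SD (5-8). Entry selection can therefore add to the arm effect or offset it.

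**The case against.** The strongest reply is that the treatment comparison is intact. The arm is chosen before randomization, so the expected shift is equal in all three groups and cancels in between-group change. The unpaired tests in 12.1 compare follow-up values, all read on the chosen arm, and need no baseline. The placebo group exists to expose this kind of shared drift. All of that stands. A reader might infer that the nebivolol-atenolol or nebivolol-placebo BP contrast is biased, or that C2 is touched; the documents support neither.

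Second, the schema lists BP at month 0. If that means a fresh reading on the chosen arm, the bias vanishes. The table makes this the less likely reading, but it is not excluded, so the absence of a Baseline BP should not be treated as certain.

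Third, the bias is not unconditional. With a two-arm reference and no true inter-arm difference it is zero. With small reading error and a higher-arm reference it is close to nominal (0.33 mm Hg, 5-6%). Even in the middle case, 86-90% of untreated groups would not reach P<0.05, so it would be wrong to say that all three groups will show a spurious change.

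Fourth, a reader might infer that the RDS shifts as well. That is possible in principle, but the documents give no BP cut-points for the 0/1/2 score, so it cannot be quantified.

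What survives is narrower. The within-group paired tests are prespecified, objective 4.2.2 looks at component changes in every treatment group, and their reference value is undefined. Following the higher arm is not itself at issue; reusing the readings that selected it as the reference is.

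**Conclusion.** The point holds for within-group BP change only. As scheduled, that change carries an arm-selection bias whose direction depends on a reference that the protocol does not define: a fall with the higher-arm mean, or a rise with the two-arm mean where true inter-arm differences exist. The size rests wholly on assumed SDs. For s of 1.5-4 and t of 0-5 mm Hg, the fall in the cases worked is roughly 0.3-2.3 mm Hg, and the net change also depends on BP entry selection. Sample size is not affected. Minor severity; worth fixing because the remedy costs almost nothing.

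**What to change.** Use the Screen readings only for eligibility and arm choice. In section 8.1, add a resting BP mark in the Baseline column. In section 8.2, specify four fresh readings on the chosen arm at Baseline, before the first dose, and name their mean as the reference for all BP changes and for the baseline RDS BP score. State which visit the two-arm measurement belongs to, and align the month-0 entry in the Study Schema with the table.

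The error in fresh readings is independent of the choice of arm, so the expected arm-selection bias is zero and the excess false positives from it disappear. This assumes that Baseline does not share arm-specific error with Screen, which is safest if the two visits fall on different days.

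The cost is a few cuff readings at a visit where standing BP is already taken for the treadmill test, plus one schedule mark. The sample size stays at 25 per arm.
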